4.6.1.3 Vital Signs

Vital signs will include measurements of temperature (axillary), respiratory rate, pulse rate, and systolic and diastolic blood pressure (BP) while the subject is in a supine position after the subject has been resting for at least 5 minutes at each visit (10 minutes for the screening visit). Vital signs should be measured prior to blood sampling. When possible, the same arm should be used for all BP measurements.

BP, respiratory rate, pulse rate, and body temperature (axillary) will be recorded at the timepoints specified in the SoA (see [Appendix 1](#)).

BP, respiratory rate, and pulse rate measurements will be performed in triplicate (can be as short as from 20-second to 1-minute intervals between measurements). The mean of three consecutive replicates will be used as the value for the defined timepoint.

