5.3.3 Assessment of Severity of Adverse Events

The WHO toxicity grading scale (see Appendix 3) will be used for assessing adverse event severity (WHO 2003). Table 2 provides guidance for assessing adverse event severity.

Table 2 Adverse Event Severity Grading Scale for Events Not Specifically Listed in WHO Toxicity Grading Scale

Severity	Severity
1	Mild; transient or mild discomfort (< 48 hours); no medical intervention or therapy required
2	Moderate; mild to moderate limitation in activity; some assistance may be needed; no or minimal medical intervention or therapy required
3	Severe; marked limitation in activity; some assistance usually required; medical intervention or therapy required; hospitalization possible
4	Life-threatening; extreme limitation in activity; significant assistance required; significant medical intervention or therapy required, hospitalization or hospice care probable

Note: Developed by the Division of Microbiology and Infectious Diseases. Regardless of severity, some events may also meet seriousness criteria. Refer to definition of a serious adverse event (see Section 5.1.2).

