Appendix 1 Schedule of Assessments (cont.)

- ^d Time matching *dosing* on Day 1.
- ^e Vital signs will include measurements of temperature (axillary), respiratory rate, pulse rate, and systolic and diastolic BP while the subject is in a supine position after the subject has been resting for at least 5 minutes at each visit (10 minutes for the screening visit). Vital signs should be measured prior to blood sampling. When possible, the same arm should be used for all BP measurements. BP, respiratory rate, and pulse rate measurements will be performed in triplicate (can be as short as ranging from 20-second to 1-minute intervals between measurements). The mean of three consecutive replicates will be used as the value for the defined timepoint.
- ^f ECGs will be collected after the subject has been in a supine position for at least 10 minutes. At the specified timepoints, 12-lead ECGs will be obtained in triplicate (i.e., three consecutive interpretable 12-lead ECGs within 5 minutes and recorded on the eCRF). Triplicate recordings should be taken for any unscheduled ECG.
- ^g Hematology will include analysis of the following: hemoglobin, hematocrit, total WBC count, differential WBC count (basophils, eosinophils, lymphocytes, monocytes, and neutrophils), platelet count, RBC, MCV, MCH, and MCHC.
- ^h Blood chemistry will include analysis of the following: A/G ratio, AST, ALT, LDH, total and indirect bilirubin, ALP, γ -GTP, CK, BUN, total protein, serum albumin, serum creatinine, uric acid, total cholesterol, triglycerides, fasting glucose, sodium, chloride, potassium, and *high-sensitivity* CRP.
- ⁱ A mid-stream, clean catch urine specimen will be collected for dipstick analysis of protein, blood, glucose, leukocytes, specific gravity, and pH. If there is a clinically significant positive result (i.e., confirmed by a positive repeated sample), urine will be sent to the laboratory for microscopy and culture. If there is an explanation for the positive dipstick result, it should be recorded, and there is no need to perform microscopy. Urine color may be evaluated from urinalysis if considered necessary.
- ^j Viral serology will include analysis of the following: HBsAg, HCV RNA or HCV Ab, and *HIV antibody*.
- ^k Immunology will include analysis of the following: non-specific IgE antibodies and anti-cardiolipin-beta-2 GPI complex antibody levels.

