Bronchospasm, Acute	transient; no Rx < 80%–70% FEV ₁ (or peak flow)	requires Rx normalizes with bronchodilator; FEV ₁ 50%–70% (or peak Flow)	no normalization with bronchodilator; FEV ₁ 25%–50% (or peak flow retractions)	cyanosis: FEV ₁ < 25% (or peak flow) or intubated
GASTROINTESTINAL				
Stomatitis	mild discomfort; no limits on activity	some limits on eating/drinking	eating/talking very limited	requires IV fluids
Nausea	mild discomfort; maintains reasonable intake	moderate discomfort; intake decreased significantly; some activity limited	severe discomfort; no significant intake; activities limited	minimal fluid intake
Vomiting	transient emesis	occasional/moderate vomiting	orthostatic hypotension or IV fluids required	hypotensive shock or hospitalization required for IV fluid therapy
Constipation	mild	moderate	severe	distensions w/vomiting
Diarrhea	transient 3–4 loose stools/day	5–7 loose stools/day	orthostatic hypotension or > 7 loose stools/day or required IV fluids	hypotensive shock or hospitalization for IV fluid therapy required

Appendix 3

WHO Toxicity Grading Scale for Determining the Severity of Adverse Events (cont.)

NEURO AND NEUROMUSCULAR				
Neuro-cerebellar	slight incoordination dysdiadochokinesis	intention tremor, dysmetria, slurred speech; nystagmus	locomotor ataxia	incapacitated
Mood	mild anxiety or depression	moderate anxiety or depression and therapy required	severe anxiety or depression or mania; needs assistance	acute psychosis; incapacitated, requires hospitalization
Neuro control (ADL = activities of daily living)	mild difficulty concentrating; no Rx; mild confusion/agitation; ADL unaffected	moderate confusion/agitation some limitation of ADL; minimal Rx	severe confusion/agitation needs assistance for ADL; therapy required	toxic psychosis; hospitalization
Muscle strength	subjective weakness no objective symptoms/signs	mild objective signs/symptoms no decrease in function	objective weakness function limited	paralysis
OTHER PARAMETERS				
Fever: oral, > 12 hours	37.7°C –38.5°C or 100.0°F–101.5°F	38.6°C–39.5°C or 101.6°F–102.9°F	39.6°C–40.5°C or 103°F–105°F	> 40°C or > 105°F
Headache	mild, no Rx therapy	transient, moderate; Rx required	severe; responds to initial narcotic therapy	intractable; required repeated narcotic therapy
Fatigue	no decrease in ADL	normal activity decreased 25%–50%	normal activity decreased > 50% can't work	unable to care for self

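### Appendix 3 fever row: Celsius readings above 40.0 and up to 40.5°C fall in both Grade 3 and Grade 4, and the two Grade 4 limits disagree

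*Combined protocol and SAP*

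**What the plan says.** Section 5.3.3 states that the WHO toxicity scale in Appendix 3 "will be used for assessing adverse event severity". Table 2 in the same section is a fallback, and only for events that the scale does not list. Fever is listed, in the Other Parameters block, in a row headed "Fever: oral, > 12 hours". Its limits are:

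- Grade 1: "37.7°C –38.5°C or 100.0°F–101.5°F"
- Grade 2: "38.6°C–39.5°C or 101.6°F–102.9°F"
- Grade 3: "39.6°C–40.5°C or 103°F–105°F"
- Grade 4: above 40°C or above 105°F

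The note closing Appendix 3 equates Grade 3 with severe and Grade 4 with life threatening. Section 3.4.2 makes the severity of adverse events a safety outcome.

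On how temperature is taken, Section 4.6.1.3 reads "Vital signs will include measurements of temperature (axillary), respiratory rate, pulse rate", and footnote e of the Schedule of Assessments agrees: "Vital signs will include measurements of temperature (axillary), respiratory rate, pulse rate, and systolic and diastolic BP". The synopsis paragraph on vital signs names tympanic temperature in its first sentence and axillary temperature in the paragraph after it. No section calls for oral measurement.

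**The concern.** A severity scale should give each measured value one grade. Here the Grade 4 range starts in Celsius below the point where Grade 3 ends, so a band of readings belongs to both. The Fahrenheit limits in the same two cells do not have this problem, so the grade can also depend on the unit used. Two people grading the same temperature could enter it as severe or as life threatening, and both would be following the protocol.

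At stake is the severity tabulation of a stated safety outcome. Section 5.7 also has the sponsor compare the severity of each event with the reference document, so an ambiguous grade could carry into that comparison.

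The route is a separate, lesser matter. The cut-offs are labelled for one measurement site, the study measures at another, and nothing links the two.

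**Working it through.** **Inputs.** Celsius and Fahrenheit limits of Grades 1 to 4 from the fever row of Appendix 3; measurement route from the synopsis, Section 4.6.1.3 and footnote e of the Schedule of Assessments.

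**Step 1: convert the Grade 3 and Grade 4 limits.** With C = (F − 32)/1.8 and F = 1.8 × C + 32:

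- 105°F: (105 − 32)/1.8 = 40.56°C
- 40.0°C: 1.8 × 40.0 + 32 = 104.0°F
- 40.5°C: 1.8 × 40.5 + 32 = 104.9°F

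The Grade 3 upper limits agree closely: 40.5°C against 40.56°C, a difference of 0.06°C. The Grade 4 lower limits do not: 40°C against 40.56°C, a difference of 0.56°C, or 105 − 104.0 = 1.0°F.

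**Step 2: grade each 0.1°C reading as printed.** The Fahrenheit value is the converted reading rounded to 0.1°F.

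| Reading (°C) | Grade by Celsius limits | Reading (°F) | Grade by Fahrenheit limits |
|---|---|---|---|
| 40.0 | 3 | 104.0 | 3 |
| 40.1 | 3 and 4 | 104.2 | 3 |
| 40.2 | 3 and 4 | 104.4 | 3 |
| 40.3 | 3 and 4 | 104.5 | 3 |
| 40.4 | 3 and 4 | 104.7 | 3 |
| 40.5 | 3 and 4 | 104.9 | 3 |
| 40.6 | 4 | 105.1 | 4 |

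The overlap is 40.5 − 40.0 = 0.5°C wide and holds five one-decimal readings. A reading of exactly 40.0°C is Grade 3 only.

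**Step 3: compare the lower boundaries of the row.** The two units also part at 37.7°C (99.9°F, just below Grade 1 in Fahrenheit), 38.6°C (101.5°F, Grade 2 against Grade 1) and 39.5°C (103.1°F, Grade 2 against Grade 3). Each is a single 0.1°C reading at a boundary, which is what rounded limits in two units produce, and in each case neither unit gives two grades. The Grade 3/4 overlap is of a different kind: it spans five readings and arises within Celsius alone. In the other numeric rows of Appendix 3, the Grade 3 and Grade 4 ranges do not overlap.

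**Step 4: check whether another rule settles it.**

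- Table 2 of Section 5.3.3 does not apply, because fever is a listed event.
- Section 5.3.5.4 has the recorded severity updated to the worst reached as an event worsens. That concerns change over time, not one reading that fits two grades.

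**Step 5: test the two printed Celsius limits as a single cut.** With one shared cut at 40.0°C, or one at 40.5°C, every 0.1°C reading from 37.7°C upward gets exactly one grade. The two choices differ only for 40.1 to 40.5°C.

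**Step 6: route.** Set side by side: Appendix 3, oral; Section 4.6.1.3 and footnote e, axillary; synopsis, tympanic and axillary. The documents give no offset between sites and no rule for grading a non-oral reading, so no size can be calculated.

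**The case against.** The strongest reply is that this hardly matters, and much of that stands. Section 5.1.2 has severity and seriousness judged independently, so a Grade 4 entry does not by itself make an event serious. Immediate reporting under Section 5.4 depends on seriousness or special interest, not on grade. No withdrawal or stopping criterion in Section 4.7 uses a fever grade. Few fevers would reach the row at all: it requires more than 12 hours' duration, Section 5.3.5.6 makes a vital-sign abnormality an adverse event only under stated conditions, and Sections 5.3.5.2 and 5.3.5.6 have the diagnosis recorded in place of its signs.

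It can also be said that the scale is an external instrument and that the slip may lie in the source or in the transcription. That cannot be checked from the documents. The row reads cleanly as extracted, and the protocol adopts it as its working tool, so a clarification is needed whatever the origin.

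Three stronger readings are tempting, and the documents do not support them:

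- A reader might infer that the grade is undefined in the band. It is doubly defined: the reading has two grades, not none.
- A reader might infer that every fever is mis-graded because oral cut-offs meet axillary readings. The documents give neither the size nor the direction of any difference between sites, and they are not uniform on the route, since the synopsis also says tympanic. The duration condition and the diagnosis rule also mean that not every fever is graded on this row. What they show is an unlinked label.
- A reader might infer from the agreement of 105°F with 40.5°C that 40.5°C is the intended cut. That shows which printed figures agree with each other, not which was meant.

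**Conclusion.** The fever row is wrong as printed. Celsius readings above 40.0 and up to 40.5°C are both Grade 3 and Grade 4, and the Grade 4 cell gives two limits that differ by 1.0°F. This follows from the printed limits and unit conversion alone; the only assumption is that the row was read correctly from the PDF.

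The route mismatch is a true but secondary inconsistency with no calculable effect.

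The expected impact of both is very small. Enrolment is 16 healthy men given a single dose, safety is summarised descriptively, the overlap matters only if a graded fever lies in that half-degree band, and the primary pharmacokinetic analysis is unaffected. This is a correction worth making because it is cheap, not because it threatens a conclusion.

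**What to change.** 1. Check the Grade 3 and Grade 4 fever cells against the source scale and reconcile their Celsius and Fahrenheit limits so that each reading has exactly one grade in either unit. The sponsor must decide which Celsius limit applies. If the source itself carries the overlap, a footnote can state the reading used in this study without altering the scale.
2. Align the temperature route across the synopsis, Section 4.6.1.3, footnote e of the Schedule of Assessments and the fever row, and add a sentence in Section 5.3.3 or Appendix 3 on how a reading taken by the measured route is graded.

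The cost is a corrected limit or footnote, one word in the synopsis if axillary is the intended route, and one sentence. No assessment, sample or analysis needs to be added.
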